## Table 2. Criteria to Determine Dose Escalation or Stopping

If dosing is terminated at any dose level, subjects will continue to be followed for resolution of the safety finding or until a new baseline is established. Depending on the nature of the reason for stopping dosing, the SMC will consider if the enrolled subjects can be continued at a lower dose level.

## 3.5.2. Safety Monitoring Committee (SMC)

The SMC will be composed of three members: The Investigator, Pfizer Medical Monitor and an External Medical Monitor. The External Medical Monitor will be a clinical trialist and an expert in the neuromuscular field. The External Medical Monitor will not be a member of the the Investigator's institutions (Johns Hopkins School of Medicine [JHSOM] and Kennedy Krieger Institute [KKI]) nor an employee of Pfizer. The SMC will be responsible for ongoing safety monitoring from the initiation of the study through the final study visit. Reviews will include aggregate safety, targeted medical events of special interest including liver toxicity, and serious AE data. The SMC may also complete ad hoc safety reviews. Ad hoc PK data may be provided to the SMC as requested.

Following the data review, the SMC will determine if the study should be continued with no changes, modified, or stopped (eg, due to safety). Decision to continue the study must be unanimous. Decision to stop the study can be made by any of the three members. In all other decisions, the External Medical Monitor will cast the deciding vote. The recommendations made by the SMC to modify the the study will be forwarded to JHSOM IRB for final decision. At any time the SMC may indicate that the limit of safety and/or tolerability has been reached and that any of the dose levels will be removed from the study.

The SMC will consider the following safety criteria during their safety review:

- The number of subjects who have severe AEs or serious AEs in the same organ system which are determined to be related to study medication.
- Other findings that indicate that dose escalation should be halted.

## 4. SUBJECT SELECTION

This study can fulfill its objectives only if appropriate subjects are enrolled. The following eligibility criteria are designed to select subjects for whom protocol treatment is considered appropriate. All relevant medical and non-medical conditions should be taken into consideration when deciding whether this protocol is suitable for a particular subject.

## 4.1. Inclusion Criteria

Subject eligibility should be reviewed and documented by an appropriate member of the investigator's study team before subjects are included in the study.

Subjects must meet all of the following inclusion criteria to be eligible for enrollment into the study:

- 1. Male and female patients age  $\geq 18$
- 2. Diagnosis of LGMD2I as defined by clinical presentation consistent with LGMD2I and FKRP gene testing showing biallelic alterations known or likely to be pathogenic. Diagnosis must be confirmed in subject's medical history and by genetic testing obtained during routine clinical care for diagnostic purposes as reported from an appropriate regulated laboratory using a clinically validated genetic test (genetic testing is not provided by the sponsor).
- 3. Ability to walk/run 10m
- 4. Abilit to rise from chair
- 5. Adequate hepatic and renal function on screening laboratory assessments
  - $GGT \leq upper limit of normal (ULN).$
  - Alkaline phosphatase  $\leq$  ULN.
  - Total Bilirubin  $\leq$  ULN.
  - Serum Albumin  $\geq$  LLN.
  - Serum creatinine  $\leq$  ULN.
- 6. Iron content estimate on the screening liver MRI within the normal range as determined by R2\* value (R2\*  $\leq$  139 Hz at 3.0T).
- 7. Participant must provide written informed consent for participating in study.
- 8. Participant must possess the ability, per the Principal Investigator (PI), to understand and comply with protocol instruction for the entire duration of the study.

## 4.2. Exclusion Criteria

Subjects presenting with any of the following will not be included in the study:

- 1. Known cognitive impairment or behavioral issues that would impede the ability to provide informed consent or to follow study instructions.
- 2. History of major surgical procedure within 6 weeks of signing the informed consent or planned surgery during the study.
- 3. Any injury which may impact functional testing. Previous injuries must be fully healed prior to consent. Prior lower limb fractures must be fully healed and at least 3 months from injury dates.
- 4. Previous treatment with another investigational product within 30 days or 5 half-lives, (whichever is longer) prior to consenting.
- 5. Corticosteroid treatment within 3 months prior to consenting.
- 6. Compromised cardiac function (left ventricular ejection fraction <50%).
- 7. Unwilling or unable (e.g. metal implants, requires sedation) to undergo examination with closed MRI without sedation.
- 8. History of allergic or anaphylactic reaction to a therapeutic or diagnostic protein.
- 9. Female subjects who are pregnant or nursing.
- 10. Subjects who, are biologically capable of having children who are unwilling or unable to use highly effective methods of contraception (as outlined in this protocol) during sexual activity for the duration of the study and through completion of final study visit.
- 11. Predisposition to iron accumulation. (Serum iron >1.2 X ULN, serum ferritin >1.2 ULNN).
- 12. Underlying disposition for bleeding disorder on screening laboratory assessment (PT/INR>1.25 X ULN, aPTT > 1.25 ULN, fecal occult blood is positive)
- 13. Evidence or history of clinically significant hematological, renal, endocrine, pulmonary, gastrointestinal, cardiovascular, hepatic, neurologic, or allergic disease.
- 14. Unwillingness or inability to comply with the requirements of this protocol (in the opinion of the PI) including, but not limited to, the presence of any condition (physical, mental, or social) that is likely to affect the participant's ability to return for study visits or adhere to the visit schedule.

Note: Screening laboratory tests with results considered by the investigator to be transient and inconsistent with the subject's clinical condition may be repeated once during the screening period for confirmation of eligibility.

#### 4.3. Enrollment Criteria

Subjects will be enrolled into the study and begin the Lead-in period, provided they have satisfied all selection criteria. Women of child bearing potential (WOCBP), must have a negative highly sensitive pregnancy test recorded within one month of initiating dosing.

## 4.4. Lifestyle Guidelines

The following guidelines are provided:

### 4.4.1. Meals and Dietary Restrictions

Subjects should maintain their normal dietary intake throughout the study with the following exceptions:

- Subjects should abstain from large amounts of caffeine within 24 hours of study visits. Negligible amounts are not of concern.
- Subjects will be asked to fast for at least 8 hours prior to collection of blood to evaluate serum ferritin, serum iron, trasferrin saturation, and TIBC.
- For at least 4 hours prior to the DXA scan, subjects should fast, or at a minimum avoid large meals. No calcium supplements should be taken within 24 hours of a DXA scan.
- Two days prior to collection of stool sample for fecal occult blood testing, *whenever possible*, subjects should refrain form eating red meat, turnips, horseradish or medications containing aspirin or vitamin C. It is recommend that subjects consume small amounts of chicken, canned tuna fish, peanuts, popcorn, bran cereal, vegetables and fruit.

## 4.4.2. Activity

Subjects should be instructed to continue with routine physical therapy including stretching or use of orthoses to prevent or minimize contractures or muscle deformities.

Subjects will be instructed to maintain normal activity levels and avoid activities that are not part of their normal daily routine within 24 hours of study visits where imaging or functional assessments will be performed.

#### 4.5. Rater Qualifications

### 4.5.1. Columbia-Suicide Severity Rating Scale (C-SSRS)

Clinical staff must be trained to complete the C-SSRS. Training is web-based and available on Columbia's Training Campus. Upon completion a certification will be provided to the trained individual.

Should a risk of suicide ideation or behavior be identified during completion of the C-SSRs, the risk assessment for the C-SSRS must be then performed by a clinically qualified mental health provider (MHP). In the United States, clinically qualified MHPs include the following: (1) general psychiatrists, (2) Psy.D or Ph.D. level Clinical Psychologists, (3) licensed Master's level Clinical Social Workers, or (4) licensed psychiatric Nurse Practitioners who have training and experience in the diagnosis and treatment of individuals with psychiatric disorders.

#### 4.5.2. Physiotherapists

Functional assessments including the respiratory function (FVC, FEV1, MIP and MEP) 4SC, strength (MMT, QMT), PUL, 10-meter walk/run (10 MR), 2MWT and TUG will be conducted by a trained physiotherapist.

## **5. STUDY TREATMENTS**

Subjects will be treated with IV infused PF-06252616 in this open-label, multiple ascending dose study. Please refer to the Dosing and Administration Instruction (DAI) for complete information on storage, stability, preparation and administration of drug product (PF-06252616).

Study Visit Day	1	29	57	85	113	141	169	197
Cohort 1				5mg/kg onc	e every 4 we	eks		
Study Visit Day	225	253	281	309	337	365	393	421
Cohort 1	I			40 mg/kg on	ce every 4 w	reeks		
Study Visit Day	589	617	645	673	701	729	757	
Cohort 1		EXTE	NSION PEF	RIOD : 40 mg	g/kg once ev	ery 4 weeks	1	

### Table 3.Dosing Schedule for Cohort 1

#### Table 4.Dosing Schedule for Cohort 2 and 3

Study Visit Day	1	29	57	85	113	141	169	197		
Cohort 2	20 mg/kg once every 4 weeks									
Study Visit Day	365	393	421	449 4	77 505	533	561	589		
Cohort 2	EXTENSION PERIOD: 40 mg/kg once every 4 weeks									
Study Visit Day	1	29	57	85	113	141	169	197		
Cohort 3	40 mg/kg once every 4 weeks									
Study Visit Day	365	393	421	449	477	505				
Cohort 3		EXTENSI	ON PERIC	))): 40 mg/l	g once every	4 weeks				

This study is a 3 cohort clinical trial. In a dose escalating fashion, subjects will be enrolled in one of 3 cohorts and will receive treatment on a 28 day schedule, per the Schedule of Activities. The dose will be dependent on the cohort and calculated based on the subject weight at each visit prior to each infusion.

Subjects in Cohort 1 will receive treatment with 5 mg/kg of PF-06252616 for 32 weeks and after safety and tolerability review of Cohort 1 subjects receiving 5 mg/kg and Cohort 2 subjects receiving 20 mg/kg will be escalated to 40 mg/kg of PF-06252616 for an additional 32 weeks. Subjects in Cohort 2 will receive treatment with 20 mg/kg of PF-06252616 for 32

weeks. Subjects in Cohort 3 will receive treatment with 40 mg/kg of PF-06252616 for 32 weeks. Subjects who completed the Follow-up period and opt to continue in the Extension period will receive treatment with 40mg/kg of PF-06252616 for up to 28 weeks in Cohort 1 and up to 40 weeks in Cohort 2, and 24 weeks in Cohort 3.

Subjects should be administered the investigational product within the visit window according to the Schedule of Activities. If a dosing visit cannot be conducted within the visit window, attemps should be made to bring the subject back for dosing as soon as possible; however the dosing must not occur within 2 weeks prior to the next scheduld dose. If the subject cannot return for dosing in this timeframe, the dose should be missed and the next visit should be conducted per the Schedule of Activities.

## 5.1. Allocation to Treatment

Subjects will be consecutively enrolled into cohorts. The first 4 subjects to successfully complete screening will be enrolled in Cohort 1. Following demonstration of safety in subjects enrolled in cohort 1 as described in the Section Safety Monitoring and Dose Escalation, the subsequent 8 subjects will be enrolled in Cohort 2. The final 8 subjects will be enrolled in Cohort 3.

## 5.2. Blinding

This study is open label. Subjects, investigators and pharmacists will be aware of the active treatment and dose level. As this study is planned to be conducted at the same time as a double-blind, placebo-controlled Duchenne muscular dystrophy (DMD) study is being conducted, by the same investigator, the following steps will occur to assure the blind is maintained in the DMD study:

- Subjects in the LGMD2I will be dosed in separate rooms from the pediatric subjects who are dosed in the DMD study.
- Separate research nurses will be used to infuse subjects from the LGMD2I study and the DMD study. They will not work on both studies.
- IV infusion bag, will covered with an amber sleeve
- IV drip chamber, will be covered transparent colored tape

## 5.3. Subject Compliance

Study treatment will be administered under the supervision of investigator site personnel.

## 5.4. Drug Supplies

## 5.4.1. Dosage Form(s) and Packaging

PF-06252616 will be provided by Pfizer Worldwide Research and Development (PWRD) as a lyophilized powder for injection as single use, sterile vials. The drug product is supplied in a glass vial sealed with a coated lyophylized stopper and an aluminum overseal and labeled according to local regulatory requirements. The drug product is designed to be reconstituted

with SWFI for IV infusion. The reconstituted solution of PF-06252616 is clear and colorless to slightly yellow in appearance.

Details of the drug product and preparation are provided in the DAI.

PF-06252616 will be packaged as open-label supplies. The external packaging (carton) will describe its contents indicating it as active drug product. Each carton will contain ten vials of study medication. Each carton will be packaged with a tamper-resistant seal. Pfizer must be notified of any study medication in which the tamper-resistant seal has been broken and this medication should not be used.

## 5.4.2. Preparation and Dispensing

See the DAI for instructions in how to prepare the investigational product for administration.

Investigational product should be prepared and dispensed by an appropriately qualified and experienced unblinded member of the study staff (eg, pharmacist, pharmacist technician) designated to participate in the study as allowed by local, state, and institutional guidance. Site pharmacists will receive study specific training on the obligations of the role and will sign an agreement that will be maintained in the Master File.

Subject's body weight will be measured at each visit. Weights obtained within one month may be used to calculate the dose of study drug to be administered.

Under aseptic conditions, PF-06252616 should then be prepared according to the DAI document provided by the sponsor.

## 5.5. Investigational Product Administration

Following preparation of the study treatment investigational product (PF-06252616) by the site pharmacist, the prepared product will be provided to the nurse administrator. Topical anesthetics (eg, topical lidocaine at the site of infusion) may be administered to subjects, consistent with institutional guidelines.

The IV infusion should be administered by qualified healthcare professionals trained to detect any infusion related issues. Infusion times, rates, any infusion interruptions or infusion rate reduction, will be recorded. The study drug should be infused over a 2-hour period where time 0 is the beginning of the infusion. The infusion time will be recorded, but the flush time will not be reported.

Should subjects experience any infusion site reaction during the IV infusion period, the treatment administration should be interrupted and supportive care should be provided according to the investigator's standard practice (eg, treatment with an antihistamine). Treatment administration may resume if the reaction resolves. Following the interruption at the discretion of the investigator, the infusion rate may be decreased to half the required rate (eg, decreased from 50mL /hr to 25mL/hr or duration may be increased from 2 to 4 hours). If the infusion rate should be decreased, the window for delivery ( $\pm$  15 minutes) will not be applied. Should the infusion be decreased, the PK will be collected per the Schedule of Activities. The duration of the treatment interruption should not exceed the limits of stability

of the drug product solution per the DAI. Consult the DAI for detailed instructions regarding study drug preparation, stability and administration. No more than 1 treatment interruption should occur during any single infusion.

Subjects should be observed for 1 hour following completion of the investigational product administration.

## 5.6. Investigational Product Storage

The pharmacy personnel, (eg, pharmacist, pharmacy technician) will ensure that all investigational products are stored in a secured area with controlled access under recommended storage conditions and in accordance with applicable regulatory requirements.

Upon receipt at the study site, the investigational products (PF-06252616) must be stored in a 2 to 8°C temperature-monitored refrigerator and in the original carton, according to labeled storage conditions. The investigational product cannot be used after the expiration date. Please refer to the DAI for complete information on storage, handling and stability of the investigational products both prior to and following reconstitution.

Storage conditions stated in the single reference safety document (SRSD) (ie, Investigator's Brochure [IB]) will be superseded by the storage conditions stated in the labeling.

Site systems must be capable of measuring and documenting (for example, via a log), at a minimum, daily minimum and maximum temperatures for all site storage locations (as applicable, including frozen, refrigerated and/or room temperature products). This should be captured from the time of investigational product receipt throughout the study. Even for continuous monitoring systems, a log or site procedure which ensures active daily evaluation for excursions should be available. The operation of the temperature monitoring device and storage unit (for example, refrigerator), as applicable, should be regularly inspected to ensure it is maintained in working order.

Any excursions from the product label storage conditions should be reported upon discovery. The site should actively pursue options for returning the product to labeled storage conditions, as soon as possible. Deviations from the storage requirements, including any actions taken, must be documented and reported to Pfizer.

Once an excursion is identified, the investigational product must be quarantined and not used until Pfizer provides documentation of permission to use the investigational product. Specific details regarding information the site should report for each excursion will be provided to the site.

Receipt of materials, door opening and closing, and other routine handling operations where the product(s) are briefly out of labeled temperature range are not considered excursions.

## 5.7. Investigational Product Accountability

The investigator's site must maintain adequate records documenting the receipt, use, loss, or other disposition of the investigational product.

### 5.8. Destruction of Investigational Product Supplies

Pfizer or designee will provide guidance on the destruction of unused investigational product (eg, at the site). If destruction is authorized to take place at the study site, the investigator must ensure that the materials are destroyed in compliance with applicable environmental regulations, institutional policy, and any special instructions provided by Pfizer and all destruction must be adequately documented.

### **5.9.** Concomitant Treatment(s)

- Subjects will abstain from all prohibited concomitant medications, except if required for treatment of AEs.
- All concomitant medications taken during the study will be recorded with the indication and start and stop dates of administration. All subjects will be questioned about concomitant medications at each visit.
- Medications taken within 28 days prior to Day 1 will be documented as prior medication. Medications taken from the time of Day 1 will be documented as concomitant medications.

### 5.9.1. Permitted Therapies

- Subjects will be permitted to receive ACE inhibitors, ARB (angiotensin II receptor blocker), aldosterone blocker and/or β blockers; however, subjects must have initiated treatment more than 3 months prior to screening and plan to remain on a stable dose during the study.
- Supplements such as vitamin D, coenzyme Q10, carnitine, aminoacids (glutamine, arginine), anti-inflammatory/anti-oxidants (eg, fish oil, vitamin E, green-tea extract) are permitted but must be be initated more than 3 months prior to screening and remain stable during the study. Calcium is permitted but should not be taken with 24 hours of a DXA scan. Multi-vitamin without iron is permitted.

#### **5.9.2.** Prohibited Therapies

The following are prohibited from the time of signing the informed consent through the final study visit.

- Immunosuppressant therapy (including glucocorticosteroids).
- Other investigational therapies.
- Androgens or human growth hormones current and in the past 3 months. Testosterone replacement in hypogonadal males will be permitted as long as the subject has been on a stable dose for the past 3 months prior to enrollment and is anticipated to remain on a stable dose for the length of the study.
- Multi-vitamin with iron or iron supplements.

## 5.9.3. Rescue Medication

Should subjects experience an infusion site reaction during the IV infusion period, the treatment administration should be paused for the subject and supportive care should be provided according to the investigator's standard practice (eg, treatment with an antihistamine).

## 6. STUDY PROCEDURES

Every attempt should be made to schedule the visits on the day specified in the Schedule of Activities. In order to provide optimal testing conditions and consistency in endpoint measurements, at visits when the functional assessments, imaging and clinical laboratory assessments are scheduled to be completed at the same visit, the visit should be completed on two days within the visit window and at approximately the same time of day in the order described below.

There is no window for Day 1(first dosing day). The visit window for the additional treatment visits is  $\pm 3$  Day. For the final follow up visit, the window is  $\pm 3$  days. The window for the PK assessments post dosing at 2 hours is  $\pm 30$  minutes. If the infusion rate is decreased (following an infusion site reaction) the PK/PD assessment should be collected at the time of infusion completion and flush (within a  $\pm 30$  minute window). Subjects are required to be observed for 1 hour after administration of PF-06252616.

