- d. Pregnancy tests (highly sensitive urine or serum) and hormone testing will only be conducted for women of child bearing potential (WOCBP). In addition, diary cards will be used to collect the first day of menstrual cycle for WOCBP.
- e. Weight collected within a month of the visit can be used to calculate the appropriate dose by body weight.
- f. Vital sign evaluations will include supine blood pressure, pulse rate, respiratory rate and oral temperature.
- g Clinical laboratory tests include hematology with complete blood count and differential, comprehensive metabolic panel (sodium, potassium, chloride, carbon dioxide, blood urea nitrogen, creatinine, calcium, glucose, total protein, albumin, total bilirubin, AST, ALT, alkaline phosphatase), cardiac troponin I, gamma-glutamyl transferase (GGT), prothrombin time (PT), activated partial thromboplastin time (aPTT), creatine kinase, amylase and urinalysis. If total bilirubin is abnormal, direct bilirubin will be tested reflexively. The samples for serum ferritin, serum iron, transferrin saturation and TIBC should be collected in the morning following an 8 hour fast.

- h. Hormone testing will include LH, FSH and estrogen in female subjects only.
- i. Fecal Occult Blood testing will be performed at home within 1 week of the scheduled visit.
- j. MRI of skeletal muscle will include a Whole Body MRI and a dedicated thigh MRI.
- k Investigational product should be delivered in a 2 hour window ±15 minutes not including the flush time. Subjects are required to be observed for 1 hour after the infusion of the investigational product is completed. If a dosing visit cannot be conducted within the visit window, attempts should be made to bring the subject back for dosing as soon as possible; however the dosing must not occur within 2 weeks prior to the next scheduled dose. If the subject cannot return in this timeframe, the dose should be missed and the next visit
-  PK/PD assessments will occur predose and 2 hours post dose. The window for the PK /PDassessments post dosing at 2 hours is + 30 minutes If the infusion rate is slowed (following an infusion site reaction) the PK/PD assessments should be collected at the time of infusion completion (+30 minutes).

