#### 9.2.4. Analysis of Pharmacokinetics

The PK concentration population is defined as all enrolled subjects who received at least 1 dose of PF-06252616 and in whom at least 1 concentration value is reported. The following PK concentrations for PF-06252616 following administration of PF-06252616 will be characterized.

Parameter	Definition	Method of Determination
C max	Maximum serum concentration	Observed directly from data as the end of infusion concentration
C trough	Trough (predose) serum concentration	Observed directly from data

No formal inferential statistics will be applied to PK data.

The serum PF-06252616 concentrations will be summarized through appropriate data tabulations, descriptive statistics, and graphical presentations which will be detailed in the statistical analysis plan. Briefly, serum concentrations for PF-06252616 will be listed and summarized descriptively by nominal PK sampling time and dose.

Any population PK analysis if conducted will be reported separately.

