8.2.3.3. Pharmacokinetic parameters

Nominal PK sampling times will be used in the derivation of PK parameters.

If a PK parameter cannot be derived from a subject's concentration data, the parameter will be coded as NC (i.e. not calculated). (Note that NC values will not be generated beyond the day that a subject discontinues.)

In summary tables, statistics will be calculated by setting NC values to missing; and statistics will not be presented for a particular treatment if more than 50% of the data are NC. For statistical analyses (i.e. analysis of variance), PK parameters coded as NC will also be set to missing.

If an individual subject has a known biased estimate of a PK parameter (due for example to an unexpected event such as incomplete administration of the IV infusion dose), this will be footnoted in summary tables and will not be included in the calculation of summary statistics.

The PK parameters will be listed and summarized for subjects in the PK parameter analysis set. Parameters will be summarized by cohort and dose. Each PK parameter will include the set of summary statistics as specified in the table below:

Parameter	Summary Statistics
Cmax, Ctrough,	N, arithmetic mean, median, cv%, standard deviation, minimum, maximum, geometric mean, geometric CV%

Table 3.PK Parameters

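### Section 6 lets the end-of-infusion PK sample be drawn up to 30 minutes early, against the +30-minute footnote, so a mid-infusion value can be reported as Cmax

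*Protocol*

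**What the plan says.** Two places in the protocol give a window for the same sample.

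- **Section 6 (Study Procedures), normal infusion:** "The window for the PK assessments post dosing at 2 hours is" ±30 minutes. For a slowed infusion, "the PK/PD assessment should be collected at the time of infusion completion and flush", again within ±30 minutes.
- **Schedule of Activities, footnote l:** "The window for the PK /PDassessments post dosing at 2 hours is + 30 minutes". For a slowed infusion it asks for the sample at completion, again with +30 minutes only.

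The visit instructions (Sections 6.3, 6.5 and 6.7) list the sample among the post-dosing procedures, at the end of infusion, hour 2.

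The clock and the infusion length come from Section 5.5, "The study drug should be infused over a 2-hour period where time 0 is the beginning of the infusion", and from footnote k, "Investigational product should be delivered in a 2 hour window ±15 minutes not including the flush time".

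Cmax is a secondary PK endpoint (Section 2.2.2.1). Section 9.2.4 defines it as "Observed directly from data as the end of infusion concentration". SAP Section 8.2.3.3 adds: "Nominal PK sampling times will be used in the derivation of PK parameters".

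**The concern.** With time zero at the start of the infusion, hour 2 is the planned end of infusion. Thirty minutes before that is 1.5 h, when part of the dose is still in the bag. Section 6 counts such a sample as in window. Footnote l and the visit sections do not.

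One post-dose sample defines Cmax at each dosing visit with PK collection (Visits 3, 5, 7 and 9, and Visits 11, 13, 15 and 17 in Cohort 1). No later sample on the same day could reveal that the peak was missed. The error goes one way: a sample drawn before the end of infusion makes Cmax too low. At stake is the accuracy of the descriptive Cmax summaries by cohort and dose, and of any PK data the Safety Monitoring Committee asks for ad hoc (Section 3.5.2).

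**Working it through.** The documents give no figure for the effect of sampling early, so there is none to reproduce. The Table 1 values used below are consistent with one another: 2690/156 = 17.2, 2690/598 = 4.5 and 2690/1200 = 2.2, as printed.

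**Inputs.** Infusion length T = 2 h, tolerance 1.75 to 2.25 h (footnote k). Slowed infusion up to 4 h (Section 5.5). Earliest sample under Section 6: t = 1.5 h, or 30 minutes before completion if slowed. Volume of distribution V = 56 to 78 mL/kg and terminal half-life about 12 to 19 days (Section 1.8). Predicted steady-state Cmax at 40 mg/kg = 1200 µg/mL (Table 1, Section 1.10).

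**Assumptions.** Constant infusion rate, the dose mixing in the stated volume, and a sample at the extreme early edge of the window.

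**Step 1: share of the dose given, f = t/T.**
- 2 h infusion: 1.5/2 = 75%, so 25% is missing.
- 2.25 h infusion: 1.5/2.25 = 66.7%, so 33% is missing.
- 1.75 h infusion: 1.5/1.75 = 85.7%, so 14% is missing.
- 4 h infusion: 3.5/4 = 87.5%, so 12.5% is missing (ignoring flush time).

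**Step 2: first dose.** There is no drug on board before the dose, so Cmax is low by 1 − f: 25% for a 2 h infusion, 33% for 2.25 h.

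**Step 3: steady state at 40 mg/kg.** Shortfall = (1 − f) × (dose/V) / Cmax.
- Rise from one dose: 40,000/78 = 513 µg/mL, to 40,000/56 = 714 µg/mL.
- 2 h infusion: 0.25 × 513 = 128 and 0.25 × 714 = 179, so 1200 would read 1072 to 1021, which is 10.7% to 14.9% low.
- 2.25 h infusion: one third of the rise is 171 to 238, so 1200 would read 1029 to 962, which is 14% to 20% low.
- Sensitivity: if the early central volume were 40 mL/kg (my assumption, not in the documents), the rise is 1000 µg/mL and the 2 h shortfall is 250/1200 = 21%.

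**Step 4: the late side, for comparison.** A sample 30 minutes late loses 1 − 0.5^(0.5/(24 × 12)) = 0.12% with a 12-day half-life and 0.08% with 19 days. If an early distribution half-life of 1 to 0.5 day is assumed, the loss is 1.4% to 2.9%. Nearly all the error is therefore on the early side.

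**Step 5: does footnote l close the gap?** Not fully. For a normal infusion it is tied to hour 2, not to completion. A 2.25 h infusion sampled at 2.0 h satisfies it with 2/2.25 = 88.9% of the dose given, 11% short.

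**The case against.** The strongest reply is that staff would not draw the sample mid-infusion. The visit sections place it after dosing, the Section 6 sentence itself speaks of post-dosing sampling, and Section 7.3 asks for the exact nominal time according to the Schedule of Activities, where the window is one-sided. Section 5.5 also refers PK timing for slowed infusions to the Schedule. This stands: an early draw is permitted by one sentence, not planned. It also shows that Section 6 is the passage out of line.

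A reader might infer that nothing in the SAP would correct an early sample. That is too strong. SAP 8.2.3.2 sets a concentration to missing in summaries when the timing deviation is judged serious enough or the pharmacokineticist flags it. SAP 8.2.3.3 leaves parameter estimates known to be biased out of the summary statistics. SAP 8.2.3.4 lists actual collection and dosing times, and Section 5.5 has infusion times recorded, so an early draw can be found. These exclusions are discretionary and carry no numeric limit, however, and may not be applied to a sample that the protocol itself calls in window.

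Could the plain plus in footnote l be a ± that lost its underline? Footnote k, just above it, prints ±15, and footnote l shows a plain plus twice, so I read it as one-sided. If it were two-sided, the conflict with the visit sections would remain.

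**Conclusion.** The inconsistency is real and should be removed, but its consequence is limited. Section 6 accepts a sample drawn during the infusion, and that value could be reported as Cmax. At worst, Cmax is about 25% low at first dose (33% for a 2.25 h infusion) and about 11% to 15% low at 40 mg/kg steady state with a 2 h infusion. These sizes rest on a constant rate, simple mixing in the stated volume although Section 1.8 describes a bi-phasic profile, and a draw at the very edge of the window. A cohort mean would move this far only if every subject were sampled that early.

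A reader might go on to infer that the exposure margin over the toxicology limit would be overstated, since 2690/1072 = 2.5 and 2690/1021 = 2.6 against the stated 2.2. The documents do not support that. The Table 1 margins are predictions from a model built on healthy-volunteer data, and neither document plans to recompute them from observed Cmax. Escalation rests on the committee's safety review and liver R2*. Section 9.2.4 excludes formal inference on PK data. No test, stated margin or sample size changes.

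**What to change.** Reconcile the passages, tying the sample to the recorded end of infusion rather than to the clock.

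1. Section 6: replace both ±30-minute windows, for normal and for slowed infusions, with 0 to +30 minutes after the recorded end of infusion.
2. Footnote l: for normal infusions, use the same anchor in place of hour 2. Copying the present footnote into Section 6 would not be enough, because it still accepts a draw at 2.0 h of a 2.25 h infusion.
3. SAP 8.2.3.3: state that any post-dose sample drawn before the recorded end of infusion is not evaluable for Cmax.

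The cost is three small protocol edits, one SAP sentence and perhaps a few non-evaluable samples. Infusion times and actual sampling times are already to be captured, so no new data are needed.
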